5.7.3. Population PK and PK/PD Analysis

In a separate analysis and report, ALXN2050 concentrations will be analyzed by both population PK and exposure-response approaches.

5.7.4. Biomarker Analyses

The following biomarker related objectives are defined in the protocol:

- Secondary objective: To assess the effect of FD inhibition on complement biomarkers
- Exploratory objective: To assess the effect of FD inhibition on AChR antibody titers in participants with gMG
- Exploratory objective: To characterize nongenetic biomarkers in adult participants with gMG

Samples will be collected for analyses that may include, but are not limited to, evaluation of complement components (eg, FD, C3, and CP activity), anti-AChR antibody, and other nongenetic exploratory biomarkers (eg, anti-MuSK antibodies, anti-LRP4 antibodies, MMP-10, and IL-6) in adult participants with gMG.

For the secondary endpoints (eg, FD, C3, and CP activity), absolute value and change from Baseline will be summarized descriptively. For the abovementioned exploratory biomarker endpoints, a stand-alone biomarker analysis plan will be developed with more details.

Baseline is defined as the last available assessment before the first dose of study intervention (predose Day 1 or Screening, whichever is the later and available).

If there is sufficient biomarker data for analysis, during Analysis 1 (Week 8), all biomarker results will be listed by treatment group and visit using the SS. Summary statistics for each variable (absolute and change from Baseline) will be provided by treatment group and visit using the FAS.

During Analysis 2 (Week 34), all biomarker results will be listed by treatment group and visit using the SS. Summary statistics for each variable (absolute and change from Baseline) will be provided by treatment group and visit using the FAS.

5.7.5. Hospitalizations

Hospitalization data will be listed by treatment group using the SS at Analyses 1 and 2.

5.8. Interim Analyses

Not applicable.

5.9. Final Analyses

The final analysis will be conducted at the end of the study. The OLES will be used for the final analysis, unless otherwise specified.

The following efficacy data collected during the OLE Period will be listed and summarized in descriptive statistics by dose level, which is the dose received at the specific visit during the OLE Period:

- Change from Baseline in the MG-ADL total score
- Proportion of participants with at least a 2-, 3-, 4-, 5-, 6-, 7-, or 8-point improvement in the MG-ADL total score
- Change from Baseline in the QMG total score
- Proportion of participants with at least a 3-, 4-, 5-, 6-, 7-, or 8-point improvement in the QMG total score
- MGFA-PIS status
- Change from Baseline in the Neuro-QoL Fatigue total score
- For efficacy and nonefficacy endpoints, baseline is defined as the last measurement on or prior to the first dose of the PEP.

AEs will be analyzed and reported in terms of TEAEs, which are defined as any AEs that started or worsened in severity on or after the first dose of study intervention through 30 days after the last dose of study intervention.

AE data will be listed and summarized in an aggregated manner (combining data from the PEP, ETP, and OLE Period) by dose received using the SS. Additional safety data collected by study visit during the OLE Period will be listed and summarized by dose level, which is the dose received ("ALXN2050 180 mg bid" and "ALXN2050 120 mg bid") at the specific visit during the OLE Period.

Available PK, PD, and biomarker data during the OLE Period will be listed using the OLES.

Description of additional analyses may be provided in a SAP addendum before the conduction of the final analysis.

6. **SUPPORTING DOCUMENTATION**

6.1. Appendix 1: Technical Specifications for Derived Variables

The following derived data will be calculated prior to the analysis.

6.1.1. Age

Age will be presented as the number of years between the year of birth and the year of the reference date. The following ages (in years) may be computed using the formula (reference year - year of birth + 1), with reference dates indicated as follows:

| Age | Reference Date |
|---|-----------------------|
| Age at informed consent | Year of signing ICF |
| Age at randomization | Year of randomization |
| Age at myasthenia gravis (MG) diagnosis | Year of MG diagnosis |

6.1.2. Definition of Baseline Values

Baseline is defined as the last nonmissing assessment value prior to the first dose of study intervention for Group 1, 2, and 3. For Group 3a and 3b, 2 baselines are defined: the PEP baseline is defined as the last available assessment prior to the first dose of placebo and the ETP baseline is defined as the last available assessment prior to the first dose of ALXN2050.

For QMG, in the event that cholinesterase inhibitor was not withheld for at least 8 hours prior to administration of the QMG test at Day 1, the Screening Visit assessment will be used as Baseline. If cholinesterase inhibitor was not withheld for at least 8 hours for these visits (both Day 1 and Screening Visits), the Day 1 assessment will be used as baseline.

6.1.3. Change From Baseline

Change in values from Baseline will be calculated as follows:

Change in value = (subsequent value - baseline value), given that both the baseline value and the subsequent value are nonmissing.

6.1.4. Percent Change From Baseline

Percent change in values from Baseline will be calculated as follows:

% change in value = (subsequent value - baseline value) / (baseline value) \times 100, given that the baseline value is nonmissing and nonzero and the subsequent value is nonmissing.

6.1.5. Analysis Visits

Summaries over post-Baseline timepoints or analyses at specific post-Baseline timepoints will be performed based on the nominal visits as collected from the eCRF and as described in the schedule of assessments in the protocol.

6.1.6. Adverse Events

The analysis of AEs is described in detail in Section 5.6.1.2.

TEAEs are any AEs that started or worsened in severity on or after the first dose of study intervention through 30 days after the last dose of study intervention. If the start date of an AE is partially or completely missing and the end (stop) date and time of the AE do not indicate that it occurred prior to the first dose, then the determination of treatment-emergent status will be based on the following:

- If the start year is after the year of the first study intervention dose, then the AE is treatment emergent; else,
- If the start year is the same as the year of the first study intervention dose and The start month is missing, then the AE is treatment emergent, else if
 - The start month is present and is the same or after the month of the first study intervention dose, then the AE is treatment emergent; else,
- If the start date is completely missing, then the AE is treatment emergent. All other AEs are considered pretreatment AEs.

AEs with missing relationship will be assumed to be related to study treatment. AEs with missing toxicity grade will be summarized as a separate category.**Imputation rule for missing date**

Missing or incomplete partial start dates and/or stop dates will be imputed following the rules as defined below. The start date will be imputed first when the start date and stop date are both incomplete partial for a participant. If the field of year is missing, then no value will be imputed. The following rules will be applied to impute the incomplete partial start date, assuming that the year is available.

Missing or incomplete partial AE start dateIf the stop date is nonmissing and the imputed start date is after the stop date, the start date will be imputed by stop date.Missing day and month

- If the year is the same as the year of the first study treatment day, then the day and month of the first treatment day will be assigned to the missing fields. If the year is not equal to the year of the first study treatment day, then "January 01" will be assigned to the missing fields. Missing day onlyIf the month and year are the same as the year and month of the first study treatment day and the AE stop date is nonmissing, then the smaller AE stop day or the first study treatment day will be assigned to the missing day. If the month and year are the same as the year and month of the first study but the AE stop day is missing, then the first study treatment day but the AE stop day is missing, then the first study treatment day will be assigned to the missing day. If the month and year are the same as the year and month of the first study treatment day but the AE stop day is missing, then the first study treatment day will be assigned to the missing day.
- 3. Missing year onlyLeave as missing.

Missing or incomplete partial AE end date

• Leave as missing.

6.1.7. Concomitant Medication/Therapies

The analysis of concomitant medications and therapies is described in detail in Section 6.2.4.

Concomitant medications or therapies are defined as any nonstudy medications or therapies that were taken or given while the participant also received study intervention. A medication or therapy will be considered concomitant if the start date is on or after the date of the first dose of study intervention or if the start date is before the first dose of study intervention and the end (stop) date is after the first dose of study intervention. If the start date of a medication/therapy is partially or completely missing and the end (stop) date of the medication/therapy does not indicate that it ended prior to the first dose of study intervention, then the determination of the concomitant status will be based on the following:

- If the start year is after the year of the first dose of study intervention, then the medication/therapy is concomitant; else,
- If the start year is the same as the year of the first dose of study intervention and
 - The start month is missing, then the medication/therapy is concomitant; else,
 - If the start month is present and is the same or after the month of the first dose of study intervention, then the medication/therapy is concomitant; else,
- If the start date is completely missing, then the medication/therapy is concomitant

All other medications/therapies are considered prior medications/therapies.

Missing or incomplete partial concomitant medication start date

If the stop date is nonmissing and the imputed start date is after the stop date, the start date will be imputed by the stop date.

Imputation rule for missing date

The start date will be imputed first when the start date and stop date are both incomplete partial for a participant. If the stop date is nonmissing and the imputed start date is after the stop date, the start date will be imputed by the stop date.

Missing or partial concomitant medication start date

- 1. Missing day only
 - If the month and year are not the same as the year and month of the first study treatment day, then "01" will be assigned to the missing day.
 - If the year is the same as the year of the first study treatment day
 - If the month is not the same as the month of the first study treatment day, then "01" will be assigned to the missing day.
 - If the month is the same as the month of the first study treatment day and the medication stop day is after the first study treatment day, then the first study treatment day will be assigned to the missing day.
 - If the month is the same as the month of the first study treatment day and the medication stop day is prior to the first study treatment day, then the medication start day will be assigned to the missing day.
- 2. Missing day and month

- If the year is not the same as the year of first study treatment day, then then "January 01" will be assigned to the missing fields.
- If the year is the same as the year of the first study treatment day
 - If the medication stop day is after the first study treatment day or the medication is "Meningococcal Vaccination," then the first study treatment day and month will be assigned to the missing fields.
 - If the medication stop day is prior to the year of first study treatment day, then medication stop day will be assigned to the missing fields.
- 3. Missing day, month, and year
 - If the medication is not "meningococcal vaccination," then the earliest date of informed consent date, the first study treatment date, or the AE end date will be assigned to the missing concomitant medication start date.
 - If the medication is "meningococcal vaccination," then the first study treatment date will be assigned to the concomitant medication missing start date.

Missing or incomplete partial concomitant medication end date

If the start date is nonmissing and the imputed stop date is before the start date, then the imputed stop date will be equal to the start date. If the "meningococcal vaccination" end date is missing, no imputation will be implemented.

- 1. Missing day only
 - If the month and year of the incomplete partial stop date are the same as the month and year of the last study treatment day, then the last study treatment day will be assigned to the missing day.
 - If the month and year of the partial incomplete stop date are not the same as the month and year of the last study treatment day, then the last day of the month will be assigned to the missing day.
- 2. Missing day and month
 - If the year of the partial incomplete stop date is the same as the year of the last study treatment day, then the day and month of the last treatment day will be assigned to the missing fields.
 - If the year of the partial incomplete stop date is not same as the year of the last study treatment day, then December 31 will be assigned to the missing fields.
- 3. Missing day, month, and year
 - If the medication is "ONGOING," no imputation will be implemented.

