## 9.4.4. Prior and Concomitant Medications

For analysis and reporting purposes, any medication started prior to first dose of study intervention will be considered prior medication, and medications that were received on or after the first dose of study intervention will be considered concomitant medications. All prior and concomitant medications including MG-specific medications and rescue therapy during the study, if any, will be summarized.

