6.2.4. Prior/Concomitant Medication

Prior medications are defined as medications taken or received by participants prior to the first study treatment. Prior concomitant MG and non-MG medications will be summarized separately using the SS and OLES.

Concomitant medications are defined as medications taken or received by participants during the study after first study treatment. (Note: Some medications may be both prior and concomitant medications). During Analysis 1 (Week 8), concomitant MG and non-MG medications used in the PEP will be summarized separately using the SS. During Analysis 2 (Week 34), concomitant MG and non-MG medications used in the PEP or ETP will be summarized separately using the ALXN2050-Treated Set. During the final analysis, concomitant MG and non-MG medications used during the OLE Period will be summarized separately using the OLES.

Medications will be coded using the WHO DD (March 2021 or higher). Medication summaries by treatment group and overall using the number and percentage of participants will be presented

by WHO-DRUG Anatomical Therapeutic Chemical Level 4 class code and by WHO-DRUG generic name.

The number (percentage) of participants using prior nondrug therapies and procedures will be summarized by SOC and PT and will be reported by the treatment group for the SS. During Analysis 1 (Week 8), concomitant nondrug therapies and procedures performed in the PEP will be summarized by SOC and PT using the SS. During Analysis 2 (Week 34), concomitant nondrug therapies and procedures performed in the PEP or ETP will be summarized using the ALXN2050-Treated Set. During the final analysis, concomitant nondrug therapies and procedures performed during the OLE Period will be summarized separately using the OLES.

By-participant listings of prior and concomitant medications and nondrug therapies and procedures will be produced by treatment group using the SS.

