1.2. Changes From Analyses Specified in the Previous Version of the SAP

- Primary endpoint: primary endpoint analyses will be performed as described in the SAP Amendment Version 1.0 Section 5.3.2. Sensitivity and supplementary analyses will not be performed.
- Secondary efficacy endpoints: only change from baseline in the QMG total score and change from baseline in the MG-ADL total score as described in the SAP Amendment Version 1.0 Section 5.4.1.1 and Section 5.4.1.3 (excluding the trend analysis to detect dose-response trend) will be performed. Descriptive summary of absolute and change from Primary Evaluation Period (PEP) baseline in MG-ADL and QMG total score will tabulate study visits through the entire study. Supplementary analyses will not be performed.
- PK/PD: PK parameter will not be reported as described in the SAP Amendment Version 1.0 Section 5.7.1.3. Population PK and exposure-response analysis will not be performed as described in the SAP Amendment Version 1.0 Section 5.7.3. All other PK/PD analyses will be performed.
- Biomarker: biomarker analysis will not be performed.
- Safety: All safety analyses will be performed as planned, as described in the SAP Amendment Version 1.0 Section 5.6 with all data collected until the end of study.
- No exploratory endpoint analyses will be performed.
- All other analyses (e.g., demographic, baseline disease characteristics, MG/non-MG medications/therapies, protocol deviation, etc), if not mentioned above, will be performed as planned.

Study exposure and adverse event data summaries will include the following two sets of analyses: (1) summary of the PEP data by Group 1, 2, 3; (2) summary of the ALXN2050 Treated Period data by Group 1, 2, 3a, 3b. Per-protocol Set and Re-randomized Set will be removed.

Medication summaries by treatment group and overall using the number and percentage of participants will be presented by WHO-DRUG Anatomical Therapeutic Chemical Level 3 class code and by WHO-DRUG generic name.

All planned listings other than the ones for exploratory biomarker endpoints will be produced.

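### SAP 6.1.7 judges incompletely dated medicines by start date alone, so a continuing medicine with a known earlier start is classed as prior and not concomitant if programmed as written

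*SAP*

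**What the plan says.** The general definition in SAP 6.1.7 is one of overlap: "Concomitant medications or therapies are defined as any nonstudy medications or therapies that were taken or given while the participant also received study intervention". Its rule for medicines begun earlier is consistent with that. They are concomitant "if the start date is before the first dose of study intervention and the end (stop) date is after the first dose of study intervention".

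A separate rule covers partial or missing start dates. It applies when the stop date "does not indicate that it ended prior to the first dose of study intervention, then the determination of the concomitant status will be based on" a list of branches. The first reads "If the start year is after the year of the first dose of study intervention, then the medication/therapy is concomitant; else". The others make the medicine concomitant when:

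- the start is in the first-dose year with the month missing;
- the start is in the first-dose year, in the first-dose month or later;
- the start date is wholly missing.

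The list ends: "All other medications/therapies are considered prior medications/therapies".

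Two other places define the term. SAP 6.2.4, which specifies the tables, says: "Concomitant medications are defined as medications taken or received by participants during the study after first study treatment". It adds that a medicine can be both prior and concomitant. Protocol 9.4.4 says: "medications that were received on or after the first dose of study intervention will be considered concomitant medications".

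The SAP Addendum, section 1.2, keeps the tables for the final report: "All other analyses (e.g., demographic, baseline disease characteristics, MG/non-MG medications/therapies, protocol deviation, etc), if not mentioned above, will be performed as planned". It changes their ATC level from 4 to 3 and leaves the classification rule alone.

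**The concern.** Whether a medicine is concomitant depends on whether it was still being taken after first dose. The branches never ask this. They look only at when it began, so a drug known to have started years earlier and still in use fails every branch, while a drug with no start date at all passes.

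The branches closely match those for treatment-emergent status in SAP 6.1.6. A start-date test suits the onset of an adverse event but not a continuing medicine. That the rule was carried over from there is an inference from the similarity.

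The tables at stake are the summaries of concomitant MG and non-MG medication, including the one for the Primary Evaluation Period (PEP) on the Safety Set. Readers use that table to see what acetylcholinesterase inhibitor, corticosteroid and immunosuppressant treatment lay behind each arm.

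**Working it through.** The plan states no figure here, so the check is to apply the rule as written.

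**Inputs.** The branches, general rule and imputation rules are from SAP 6.1.7. The first-dose date, 14 September 2022, is an assumption for illustration, and every record is taken as not known to have ended before it. The comparison column imputes the start by the SAP's own rule (first of the month, or 1 January when only an earlier year is known) and then applies the general rule with an assumed stop after first dose.

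| Recorded start | Branches as written | Impute, then general rule |
|---|---|---|
| 2015 | prior | concomitant |
| Mar 2015 | prior | concomitant |
| Dec 2021 | prior | concomitant |
| Mar 2022 | prior | concomitant |
| Aug 2022 | prior | concomitant |
| 2022, month missing | concomitant | concomitant |
| Sep 2022 | concomitant | concomitant |
| Oct 2022 | concomitant | concomitant |
| 2023 | concomitant | concomitant |
| wholly missing | concomitant | not run |

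All five records with a known start before the first-dose month change class. The other records compared do not.

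**Complete start dates.** A start of 10 March 2015 with a stop after first dose is concomitant under the general rule. The same start marked ongoing has no stop date to compare, and 6.1.7 imputes none for ongoing records. It is concomitant only through the opening definition.

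**Who is exposed.** Inclusion 5 and protocol Table 9 require at least 180 days on azathioprine, or 90 days on other immunosuppressants, before Screening. Both exceed any calendar month, so the true start of such therapy always lies in a month before first dose. The 28-day and 14-day stability periods for corticosteroids and acetylcholinesterase inhibitors do not guarantee this, although long-standing use meets it. A therapy begun after first dose always satisfies a branch if its partial date is right, so treatment started on study, including rescue, is not affected.

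**Size.** Let p be the share of background-therapy records with a partial start date, and r the share of those that a branch still catches (for example, year only in the first-dose year). The share of records lost from the concomitant class is p × (1 − r). The documents give neither value. With p assumed at 20%, 50% or 80%, the ceilings at r = 0 are 20%, 50% and 80%; with p = 0 the loss is nil. The tables count participants, so anyone with another qualifying record of the same drug is still counted.

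**The case against.** The strongest reply is that the SAP elsewhere classifies these medicines correctly. The opening definition of 6.1.7, SAP 6.2.4 with its dual-status note, and protocol 9.4.4 all make a continuing medicine concomitant. So does imputing the start and applying the general rule when there is a later stop date. Protocol 6.5 asks for start and end dates, so partial dates may be few. Records classed as prior still appear in the prior-medication summary and in the by-participant listings.

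This stands in part. It shows that the SAP contradicts itself and that the loss is not certain. It does not make the branch list safe:

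- Section 6.1.7 is in the appendix of derivation specifications and says status rests on the branches. A programmer following it would code them.
- The dual-status note allows a prior medicine to be concomitant as well, but the branches that would make it concomitant have already failed.
- The imputation route needs a stop date, and ongoing records have none.

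A reader might infer that long-standing background therapy as a whole disappears from the concomitant tables, or that the arms are distorted unequally. The documents support neither. Fully dated records never enter these branches. Background therapy predates randomisation and the PEP is blinded, so nothing suggests that date completeness depends on arm; only a chance imbalance is possible.

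**Conclusion.** The rule is wrong as written, within a narrow scope. If 6.1.7 is programmed literally, a medicine that is ongoing or stops after first dose is classed as prior and not concomitant when its start date is incomplete but known to fall in an earlier year, or in an earlier month of the first-dose year. That contradicts the section's own definition, SAP 6.2.4 and protocol 9.4.4.

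The size is unknown, from none to substantial, because it depends on the share of partial start dates and on which reading was programmed. Only descriptive medication tables change. No stated efficacy test, error rate or sample size depends on this classification, and no difference between arms is shown. It still merits correction because the Addendum carries the tables into the final report and the change is cheap.

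**What to change.** In SAP 6.1.7, replace the start-date-only branches with:

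> Any medication/therapy, with a complete, partial or missing start date, that is marked ongoing, or whose stop date (imputed if partial) is on or after the first dose, is concomitant. It is also prior if its known or imputed start is before first dose. A record with a missing stop date that is not marked ongoing is queried and, if unresolved, is treated as concomitant and flagged.

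Use the same on-or-after boundary in the general rule, which now requires a stop after first dose, so that fully and partially dated records are treated alike. The wording also settles fully dated starts marked ongoing. The query step matters because protocol 8.11.4 collects MG therapy from the 2 years before Screening. Without it, discontinued treatments with an unknown stop date could enter the concomitant table unnoticed and overstate use.

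If the tables are already programmed, confirm which reading was used and correct them for the final CSR.

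The cost is one short paragraph in the SAP, one derivation rule, and queries on records with no stop date and no ongoing mark. No new assessments are needed.
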